To increase external validity of findings, we will include participants taking psychotropic medications that have been stable for 6 weeks and expect to remain stable for the approximately 3-week intervention protocol (with the exception of those taking neuroleptic/ antipsychotic medications). Those who previously received tic-specific therapy will be included if they meet the tic severity criterion. Youth receiving other forms of psychotherapy will be included provided these treatments are not focused on tics. All concurrent treatments will be monitored during the study period.

- *8.2.* Exclusion Criteria:
 - Medical conditions contraindicated or associated with altered TMS risk profile, including history of intracranial pathology, epilepsy or seizure disorders, traumatic brain injury, brain tumor, stroke, implanted medical devices or metallic objects in the head, current pregnancy or girls of childbearing age not using effective contraception, or any other medical condition deemed serious or contraindicated by a study physician ([name] or [name]).
 - Inability to undergo MRI.
 - Left handedness.
 - Active suicidality.
 - Previous diagnosis of psychosis or cognitive disability.
 - Substance abuse or dependence within the past year.
 - Concurrent psychotherapy focused on tics.
 - Neuroleptic/antipsychotic medications.
 - Taking a medication that has not reached stability criterion (same medication and dose for 6 weeks with no planned changes over the intervention period)
- 8.3. Screening: A phonecall or secure video chat screening prior to study participation will be used to screen for inclusion/exclusion criteria. Exclusion criteria will be more thoroughly assessed during the pre-treatment assessment and by examining medical record documents. Medical history will be reviewed prior to rTMS administration using information gathered from participant/parent screening, which includes the Screening Questionnaire for rTMS Candidates questionnaire, and medical records obtained. If any potential exclusion criteria are identified where the

PROTOCOL TITLE: Transcranial Magnetic Stimulation to Augment Behavior Therapy for Tics VERSION DATE: 2/24/2022

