- 12.1. Withdrawal Circumstances: Anticipated circumstances under which participants will be withdrawn from the research without their consent include: 1) the participant does not/no longer meets inclusion/exclusion criteria; 2) study investigators decide that the participant has an emotional, physical, or behavioral reaction that poses a safety concern or interferes with data collection (e.g., poor compliance with instructions, too much anxiety to comfortably proceed with a task); 3) significantly deteriorating clinical course (e.g., emergence of acute suicidality); 4) significant adverse reaction to TMS, assessed using a TMS Symptom Rating Questionnaire daily; or 5) serious physical illness. Participants will be free to decide to withdraw at any time for any reason.
- 12.2. Withdrawal Procedures: Study withdrawals will be documented. When safe and feasible, participants who are withdrawn or who decide to terminate participation prematurely ("drop out") will be encouraged to return for a last assessment. This last assessment will consist of measures in the follow-up assessments (i.e., clinical measures only and not the MRI). We will make an attempt to provide participants with appropriate care referrals in the event of any withdrawals or drop-outs.
- 12.3. Termination Procedures: Individual participants will be considered to have completed study procedures after the 3-month follow-up assessment (or earlier as a result of drop-out or investigator-initiated withdrawal). The entire study will be complete after analysis of all identifiable data is complete. After termination of the project, only de-identified data will be used for analysis.

13. Risks to Participants

13.1. Foreseeable Risks:

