- **Premature Termination.** At any time, participants may deteriorate or develop clinical exigencies that lead study staff to recommend additional out-of-protocol treatments above and beyond that provided by ASAP guidelines (e.g., change in medications during the study). Such participants will be considered "premature terminators" (PMT) and classified as a protocol violation. In order to enhance the ITT analyses, "prematurely terminated" participants will continue to be treated within their assigned treatment arms insofar as possible, and assessments will continue according to protocol.
- Analysis population will be an intent-to-treat population including all enrolled participants who completed at least 1 CBIT session.
- Treatment of Missing Data: All participants will remain

PROTOCOL TITLE: Transcranial Magnetic Stimulation to Augment Behavior Therapy for Tics VERSION DATE: 2/24/2022

in the study unless consent is withdrawn or there are concerns about patient safety. While there is little that can be done to address missing data when participants drop out during the training process itself, we can compare baseline characteristics of those who drop out at this time versus those who do not and adjust models based on significant predictors of dropout. For those who drop out during the follow-up period or miss some assessments during followup, we will use multiple imputation by chained equations (MICE) to allow for missing data without loss of those cases from the model under the assumption of Missing at Random (MAR). Sensitivity Analysis: If dropout status appears to be Missing Not At Random (MNAR), i.e., dropout is associated with an unobserved outcome, we will run sensitivity analyses using MICE to compare imputed and non-imputed models results to assess robustness of statistical inference.

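### Sections 12.1 and 15.1 give conflicting non-safety rules on who leaves the study, and section 12.2 bars the MRI for anyone who leaves, so early leavers lose the neural primary outcome by rule

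*Combined protocol and SAP*

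**What the plan says.** **Who leaves.** Section 12.1 lists five grounds for withdrawal without the participant's consent. Item 1 is that "the participant does not/no longer meets inclusion/exclusion criteria". Item 2 covers reactions that are a safety concern or that interfere with data collection, with poor compliance as an example. Item 3 is a "significantly deteriorating clinical course (e.g., emergence of acute suicidality"), item 4 a "significant adverse reaction to TMS, assessed using a TMS Symptom Rating Questionnaire daily", and item 5 serious physical illness. Section 12.3 counts investigator-initiated withdrawal as the end of that person's study procedures.

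**Who stays.** Section 15.1, on missing data, says all participants remain "in the study unless consent is withdrawn or there are concerns about patient safety". Its paragraph on premature termination covers people who deteriorate or need treatment outside the protocol, and gives a medication change as its example. They are recorded as protocol violations but "will continue to be treated within their assigned treatment arms insofar as possible, and assessments will continue according to protocol".

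**The criterion that links the two.** Section 8.2 excludes anyone "Taking a medication that has not reached stability criterion (same medication and dose for 6 weeks with no planned changes over the intervention period").

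**What is measured on leaving.** Section 12.2 encourages people who are withdrawn or drop out to return once more when safe and feasible. It then states: "This last assessment will consist of measures in the follow-up assessments (i.e., clinical measures only and not the MRI").

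**The concern.** Staff facing one participant whose medication changes during treatment can find two instructions: withdraw (12.1) or retain and assess (15.1). The same holds for poor compliance that raises no safety issue. Which rule is followed decides whether the person has outcome data, and it could vary from case to case.

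The MRI restriction is a second and separate problem. Both statements of the neural primary outcome need the post-treatment scan: resting-state connectivity in section 3.1 and SMA activation in section 15.1, Aim 1. The grounds for leaving include deterioration, poor compliance and reaction to TMS. These are plausibly related to outcome, and reactions to TMS may differ between active and sham arms. A rule that removes the scan for exactly these people risks a biased comparison as well as a smaller one.

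**Working it through.** The check is mainly a comparison of sections.

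**Step 1: 12.1 against 15.1, ground by ground.**

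| Ground in 12.1 | Position under 15.1 | Conflict? |
|---|---|---|
| Item 1, criteria no longer met | Not a consent or safety ground; a medication change is the premature-terminator example | Yes |
| Item 2, interferes with data collection | Not a consent or safety ground | Yes |
| Item 2, safety concern | Within the safety exception | No |
| Items 3, 4 and 5 | Can be read within the safety exception | No |

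In item 1, the part about people who do not meet criteria may cover those found ineligible at the pre-treatment assessment. Under section 8.3 they stop before MRI and treatment, so they do not matter here. The part about no longer meeting criteria goes further.

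**Step 2: when the MRI rule costs data.** Table 1 places the MRI at the pre-treatment and post-treatment assessments, and section 11.4 pays for two scans. None is planned at 1 or 3 months. Section 5.2 allows 13 business days for the ten treatment visits and 10 calendar days after the last of them for the post-treatment visit. Loss therefore arises only for people who leave before that scan, and no later scan can stand in for it. Leaving during follow-up costs no neural data.

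**Step 3: the behavioural primary outcome.** Table 1 lists the Tic Suppression Task at the follow-up visits, and 12.2 uses the follow-up measures for the last assessment. The task is already covered.

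**Step 4: whether the analysis repairs the loss.** The Aim 1 model takes baseline activation as a predictor, so a person with only a baseline scan contributes no outcome. Section 15.1 describes multiple imputation for dropout or missed assessments in follow-up. For dropout during treatment it says little can be done, and offers a baseline comparison and covariate adjustment. The sensitivity analysis compares imputed with non-imputed results; the imputation is specified under missing at random.

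**Step 5: whether a power loss can be stated.** Section 15.2 gives 80% power at η² = 0.18 after expected attrition. Neither the attrition rate nor the Aim 1 alpha is given, so the figure cannot be reproduced from the plan's own inputs. Assume a three-group ANOVA and alpha 0.05, with noncentrality λ = N × 0.18/0.82:

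- N = 60: λ = 13.17, power 89.6%
- N = 48: λ = 10.54, power 80.9%
- N = 47: λ = 10.32, power 80.0%

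The stated 80% thus fits about 20% attrition (1 − 48/60). Withdrawals under 12.1 are attrition, and nothing says the allowance leaves them out. As an illustration, an assumed 2 to 6 losses from 60 leaves 58 to 54 scans and power of about 88% to 86%, above the stated 80%. If the test is read as active against sham (two groups), 80% is reached at N = 38. The documents therefore support no figure for lost power.

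**The case against.** **The specific rule governs.** Section 8.2 is worded with planned changes in mind and section 8.1 with expected stability, so an unplanned change does not plainly breach a criterion judged at entry. Section 15.1 addresses that very event, and a reader could let it override the general clause in 12.1. This is fair, and it is why the point says a medication change can fall under both rules, not that it must. It does not settle the matter: the six-week same-dose wording can be read the other way, no order of precedence is stated, and the data-collection clause in item 2 conflicts regardless.

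**The plan acknowledges early dropout, and the population is intent-to-treat.** Both are true. The population is everyone with at least one CBIT session, and withdrawal does not remove anyone from it. A reader might infer that 12.1 defeats the intent-to-treat analysis. The documents do not support that; what is lost is the neural measurement of some members of the population.

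**The loss is already budgeted.** A reader might subtract further withdrawals from the 47 or 48 scans that give 80% power, and conclude that power falls below target. That would count attrition twice unless the allowance excluded 12.1 withdrawals, which no section says.

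**All withdrawals conflict with 15.1.** This too is tempting, but the safety grounds fit the exception in 15.1.

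**Conclusion.** The point holds in two parts. First, item 1 and the data-collection part of item 2 in section 12.1 cannot both stand with section 15.1 as written. Second, section 12.2 withholds the only post-baseline scan from people who leave before it, even when they return and a scan would be safe and feasible, and section 15.1 plans no imputation for dropout during treatment.

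That the loss is selective is an inference from the listed reasons for leaving. Its size and direction cannot be computed from the documents. It is confined to departures before the post-treatment scan and to the neural primary outcome. No stated figure in the plan is shown to be wrong. This is a low-cost improvement worth making, not a flaw that invalidates the design.

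**What to change.** 1. Reconcile section 12.1 with section 15.1 so that one rule says who leaves and who stays, covering medication changes and behaviour that hampers data collection. Which rule applies is for the investigators; no view is taken here.
2. Amend section 12.2 so that anyone who leaves before the post-treatment scan is offered the already planned post-treatment MRI when it is safe, feasible and consented, and is analysed in the assigned arm. The Tic Suppression Task needs no change.

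The cost is amendment wording and a few scan visits by people who have stopped treatment. Two scans per participant are already planned (section 11.4), and section 5.2 already allows participants to be brought back for a repeat scan. The documents give participant payments, not a scanner budget, so the cost per visit cannot be stated.

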 - Timing: Consent/assent will be obtained at the first point of formal assessment (optional detailed eligibility assessment or pre-treatment assessment visit) (Step 2). Daily sessions of CBIT+TMS (Step 4) will begin within 10 calendar days of the pre-treatment assessment. Participants will complete 10 CBIT+TMS visits within 13 business days. The post-treatment visit will be completed within the 10 calendar days following the last CBIT+TMS visit. The 1-month assessment will be completed 4-6 weeks after the last CBIT+TMS visit, and the 3-month assessment will be completed 12-14 weeks after the last CBIT+TMS visit.

Table 1. Study measures		Steps in Fig 1		Time (min)			
	Steps in flow chart (Figure 1)	1	2	4	5	6,7	
MEASURE	DETAILS						
Phone Screening	Eligibility, TMS safety screen ^{38,39}	x	x				20
Medical records	Last doctor visit, current medications, relevant/available documents; used for eligibility determination	х					
MRI safety screen	Eligibility	x	x		x		5
Demographics	Sample characteristics		x				10
IQ	Eligibility		x				15
MINI 7 KID ⁴⁰ or adult ⁴¹	Structured diagnostic interview		x				30

PROTOCOL TITLE: Transcranial Magnetic Stimulation to Augment Behavior Therapy for Tics
VERSION DATE: 2/24/2022

Yale Global Tic Severity Scale, YGTSS ⁴²	Gold-standard, clinician-administered tic severity scale. Includes symptom checklist of specific tic types.	x		x	x	30
Tic Suppression Task ^{12,43}	Direct observation measure of tic suppression ability	x	x	x	×	10
Parent/Adult Tic Questionnaire ^{44,45}	Adult-self or parent-report measure of tic symptoms and severity	x		x	x	5
Premonitory Urge for Tics Scale ^{46,47}	Self-report measure of intensity of urges to tic	x		x	x	5
Child/Adult Behavior Checklist ^{48,49}	Parent- or adult-self report measuring broad emotional and behavioral functioning	x		x	x	15
Sheehan Disability Scale ⁵⁰	Self- and parent measure of functional impairment	x		x	x	10
Tic Impact questions	Self- and parent-rated measures of how tics impact daily function	x		x	x	5
Behavior Rating Inventory of Executive Function ⁵¹	Self- and parent-rated measure of impairment of executive function	x		x	x	15
Ask Suicide-Screening Questions (ASQ)	Clinician-administered screen of suicidality	х		x	x	5
TMS Adverse Effects Questionnaire ³⁹	Tracks side effects of TMS		x	x	x	5
Clinical Global Impressions (CGI)	Clinician, patient, parent-rated global measure of illness severity and improvement	x		x	x	2

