- **Potential delay of non-experimental treatment.** All participants will receive CBIT, a well-established treatment that is considered by the American Academy of Neurology to be the first-line intervention for tics.⁶ Because we exclude those with planned medication changes, participation in this study could cause a delay in effective pharmacological treatment with demonstrated efficacy.

PROTOCOL TITLE: Transcranial Magnetic Stimulation to Augment Behavior Therapy for Tics VERSION DATE: 2/24/2022

- **Confidentiality.** Personal information collected during study procedures could result in social and/or psychological risk if released inappropriately. However, this is an extremely unlikely event considering all of the protective measures and precautions taken to keep data secure (see below). Researchers will be carefully trained about the importance of confidentiality and required to undergo HIPAA training.
 - Side Effects/Adverse Events. Adverse effects will be monitored very closely throughout the study, through structured assessments and clinical interactions. At all visits involving TMS, the TMS operator will conduct a general inquiry regarding any health complaints, recent illness or injury, and need for medical consultation since the previous visit. Reported complaints will be coded on a standardized Adverse Events tracking form. Although unlikely, based on the nature of this study, the rater and study physician (Drs. [name] and [name]) will rate whether the adverse event is related to the study or not. [name] will then take relevant actions, which may include monitoring, adjunctive intervention within study protocol, or removal from the study.
- *13.2.* Reproduction Risks: Currently, the effects of rTMS on hormonal cycles and the unborn fetus are unknown, therefore negative pregnancy test results and effective contraception will be required of childbearing age female participants.
- 13.3. Risks to Others: N/A

14. Potential Benefits to Participants

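### A participant withdrawn for a TMS reaction is asked for at most one undated side-effect assessment after TMS, against three dated ones for those who continue

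*Combined protocol and SAP*

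**What the plan says.** Section 12.1 lists reasons for withdrawing a participant from the research without consent. Item 4 is a "significant adverse reaction to TMS, assessed using a TMS Symptom Rating Questionnaire daily". Section 12.2 says that people who are withdrawn or drop out, where it is safe and practicable, "will be encouraged to return for a last assessment. This last assessment will consist of measures in the follow-up assessments", meaning the clinical measures without the MRI. It gives no window for that visit, and adds: "We will make an attempt to provide participants with appropriate care referrals in the event of any withdrawals or drop-outs". Section 12.3 places the end of study procedures at the 3-month visit, "or earlier as a result of drop-out or investigator-initiated withdrawal".

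For everyone else, Table 1 schedules the TMS Adverse Effects Questionnaire ("Tracks side effects of TMS") at the TMS visits, at post-treatment and at both follow-ups. Section 13.1 sets the general standard: "Adverse effects will be monitored very closely throughout the study, through structured assessments and clinical interactions".

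Section 15.1 has a separate rule. Participants for whom staff recommend treatment outside the protocol are called premature terminators, and their scheduled assessments carry on. The missing-data paragraph in the same section keeps all participants in the study, except where consent is withdrawn or safety is a concern.

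**The concern.** Section 12 treats stopping the intervention and leaving data collection as one event. For a participant withdrawn because of a TMS reaction, the event that makes later safety data most informative also ends their scheduled collection. Whether the reaction resolved, how long it lasted and whether anything emerged later then depend on one optional visit with no date.

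Two uses of the data are affected. Section 3.2 makes the comparison of the two TMS procedures on safety and feasibility measures a secondary endpoint, and Aim 3 may use that comparison to prioritise a regimen. Follow-up that is missing because of the reaction itself is informative: a regimen with more such withdrawals supplies fewer later reports. The second use is the description of tolerability in a sample aged 12-21. When section 13.1 discusses earlier seizures in youth, it relies on outcomes at 4 and 6 months. The plan does not secure comparable information on its own withdrawn participants.

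**Working it through.** No power or sample-size figure bears on this point, so there is no stated figure to reproduce. The check sets the withdrawal rules beside the assessment schedule and counts.

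**Inputs.** Withdrawal rules: 12.1 to 12.3. Schedule: Table 1. Windows: the Timing item in 5.2, counted from the last CBIT+TMS visit. The printed columns of Table 1 are broken in the text available. The YGTSS row (pre-treatment, post-treatment, follow-ups) fixes their order, and the side-effect row then reads as TMS visits, post-treatment and the two follow-ups.

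**Planned side-effect questionnaires after the last TMS session**

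| | Continues | Withdrawn for TMS reaction |
|---|---|---|
| Post-treatment, 0-10 days | 1 | not scheduled |
| 1 month, 4-6 weeks | 1 | not scheduled |
| 3 months, 12-14 weeks | 1 | not scheduled |
| Last assessment, no date | does not apply | 0 or 1, voluntary |
| Total | 3 | at most 1 |

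The shortfall is 3 - 1 = 2 contacts if the last assessment takes place and 3 - 0 = 3 if it does not. The length of follow-up for a withdrawn participant cannot be calculated, because the visit has no date.

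**Is the gap closed elsewhere?**
- The adverse-event paragraph in 13.1 names monitoring, adjunctive intervention or removal as possible actions. It describes no follow-up after removal.
- The hearing paragraph in 13.1 provides for referral, and the seizure paragraph for acute care and further evaluation. Neither sets study follow-up.
- Premature Termination in 15.1 continues assessments, but its class is defined by a need for outside treatment, not by 12.1(4). A participant with a bad reaction could fall under either rule, and the safety exception in the missing-data paragraph points back towards leaving the study.

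**How many participants?** The documents give no expected rate. Assuming equal allocation of the 60 participants, which is not stated, each arm has 60/3 = 20. One such withdrawal would be 1/20 = 5% of an arm, and two would be 2/20 = 10%. This shows scale only and is not a forecast.

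**Effect on the regimen comparison.** Aim 3 names neither the safety variables nor the time point, and makes this comparison only if both regimens beat sham. Reports up to withdrawal are kept. The informative loss arises only to the extent that the analysis uses data collected after treatment.

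**The case against.** The strongest reply is that safety information is not switched off at withdrawal, and much of it stands. The last assessment uses the follow-up measures, so it includes the side-effect questionnaire, and 5.2 allows assessments by video. Section 13.1 has reported complaints coded on a tracking form and adverse events rated for relatedness to the study. Withdrawal is also not the only response to a reaction: intensity may be adjusted for tolerability (5.2), and 13.1 lists monitoring as an option. Anyone kept in the study has the full schedule. The DSMB charter and consent form are not among the documents available here, so a post-withdrawal rule there cannot be excluded.

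Several stronger readings are tempting, and the documents do not support them.
- A reader might infer that those harmed are followed less than anyone else. The same single assessment is offered to every early leaver, so the contrast holds only against those who continue.
- A reader might count 13 questionnaires for a completer (10 + 3) against 4 for someone withdrawn at visit 3 (3 + 1). That includes treatment-day forms for sessions the withdrawn person never had. The fair contrast begins after the last TMS session.
- A reader might infer that the DSMB would not see the problem. Section 18.2 has it review seizures, side effects, hospitalisation and premature dropout, with SAEs expedited. It may lack the later course, not the event.
- A reader might infer that Aim 3 is biased. Without a named measure or time point, bias is possible but not shown.

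The premature-terminator rule is the best textual defence. It overlaps with section 12 but does not resolve it.

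**Conclusion.** The point holds as a limited weakness that should be corrected. No available text secures information on the later course or resolution of a reaction still present at withdrawal. Follow-up is reduced rather than absent, and the effect on the regimen comparison depends on an analysis that is not yet specified.

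This rests on three assumptions: that Table 1 is read as set out above, that withdrawal under 12.1(4) means leaving data collection as 12.3 implies, and that no rule in the charter or consent form says otherwise. If section 15.1 was meant to cover these participants, the sections conflict and the text still needs an edit.

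**What to change.** Reconcile section 12 with the premature-termination and missing-data text in 15.1, so that stopping the intervention and leaving data collection are separate decisions. In 12.2 and 12.3, state that participants withdrawn for a TMS reaction, unless they or their parents decline, are still asked for the existing TMS Adverse Effects Questionnaire and the adverse-event inquiry. Use the existing post-treatment, 1-month and 3-month windows, and allow remote completion as 5.2 already does. Include these data by assigned arm in the safety summaries and DSMB reports.

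The cost is protocol wording, consent wording if needed, and a few short contacts by existing staff. Table 1 allots 5 minutes to the questionnaire, so three completions take 3 x 5 = 15 minutes per participant, plus the inquiry. The downside is some burden on families who have left treatment, and some will decline. When TMS is stopped and how reactions are managed remain with the investigators.
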